MAC	Minimum alveolar concentration
MOAA/S	Modified Observer's Assessment of Alertness/Sedation
NSR	Non-significant Risk
PI	Principal Investigator. The person responsible for overseeing the study and assuring study completion in compliance with applicable regulations.
PIC	Patient Interface Cable
PK/PD	Pharmacokinetics and pharmacodynamics
POC	Point of Care
RA	Regulatory Authority
SpO2	A non-invasive spectroscopic estimate of arterial oxygen saturation measured transcutaneously by a pulse oximeter
SAE	Serious Adverse Event
SAP	Statistical Analysis Plan
SOP	Standard Operating Procedures
TES	Tetanic Electrical Stimulation
TCI	Target-controlled infusion
TIVA	Total Intravenous Anesthesia
UADE	Unanticipated Adverse Device Effect
USADE	Unanticipated Serious Adverse Device Effect

3. Synopsis

Title	Evaluation of BIS™ and Levels of Sedation with Common Inhalational Anesthetics in Healthy Volunteers (OLIVER)
Product Name	Bispectral Index Sensor (BIS™) Complete Monitoring System
Sponsor	Medtronic Medical Surgical Portfolio Patient Monitoring OU [name]
Indication under investigation	Validation of the BIS™ index, one of the Complete Monitor output parameters, as an aid in monitoring the effects of desflurane, isoflurane and sevoflurane with balanced anesthetic techniques for adult patients.
Investigation Purpose	To investigate the relationship between BIS™ and inhaled anesthetics across a wide range of anesthetic concentration and hypnotic states, and to provide evidence to support BIS™ performance in use with isoflurane, sevoflurane and desflurane in combination with opioids.
Product Status	BIS™ is commercially available in the United States
Primary Objective	To determine BIS ₅₀ (BIS™ value at which 50% of patients will be unresponsive at a given drug concentration)
Secondary Objective(s)	To determine BIS ₉₅ (BIS™ value at which 95% of patients will be unresponsive at a given drug concentration) To determine Prediction Probability (P _K) for correctly predicting if the subject was responsive or unresponsive.
Study Design	This is a prospective, randomized study to collect data to evaluate the relationship between BIS™ and inhaled anesthetics without and with opioids. Five groups of anesthetics regimens will be studied as follow: 
1. Sevoflurane alone2. Sevoflurane with Remifentanil3. Sevoflurane with Fentanyl4. Desflurane alone5. Isoflurane alone

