	
• BIS™, Picture Recall Test (for the sevoflurane, sevoflurane with remifentanil and sevoflurane with fentanyl groups), Modified Observer's Assessment of Alertness/Sedation (MOAA/S) Assessments 
TES assessment as described above. A clinician will be monitoring respiratory and cardiac functions to determine if interventions are needed to maintain an adequate airway. The respiration support will be provided to ensure an unobstructed airway, adequate oxygenation ($\text{SpO}_2 > 92\%$), and carbon dioxide (CO_2) homeostasis throughout the study. As needed for airway support, the anesthesiologist may gently lift chin or jaw thrust (with or without manually assisted breathing), insertion of an airway device (oropharyngeal airway or laryngeal mask airway) and/or intermittent positive pressure ventilation (IPPV). Mask or nasal cannula will be used for supplemental oxygen (O_2) delivery. Any study procedures may be discontinued for the subject's safety.
 
The opioids (remifentanil and fentanyl) will be administered via the target-controlled infusion (TCI) pump using either the preprogrammed pump protocols or computer-controlled program, e.g., Total Intravenous Anesthesia (TIVA) Trainer, or another computer-controlled program, to ensure that the targeted effect-site concentration of a drug is reached and maintained at each drug concentration plateau. Remifentanil and Fentanyl diluted to a single concentration of 50 $\mu\text{g}/\text{ml}$ will be used for this study. The infusion rate between 0 and 1200 ml/hr will be used to achieve a target effect-site concentration of remifentanil and fentanyl. For remifentanil, Minto pharmacokinetics/pharmacodynamics (PK/PD) model will be used. [1] The kinetic model for fentanyl will not be weight-adjusted.[2]
 
Inhalation anesthetic drugs will be administered via a tight-fitting face mask or a laryngeal mask (LMA). Volunteers will be connected to a circular breathing system of an anesthesia machine. After the volunteer loses responsiveness, LMA may be inserted as needed to facilitate airway control at deeper levels of anesthesia. Once emergence is started, LMA should be removed at the earliest point while ensuring subject safety. Inhalation agents will be administered with O_2 to maintain saturation of greater than 90%.
 
Lidocaine can be administered per Investigator discretion as a bolus over 3-5 seconds at a maximum concentration of 100mg to aid in the infusion of propofol for subject's comfort.
 
Phenylephrine may be used prophylactically on all subjects at a concentration of 100 mcg/mL for the prevention of hypotension as a result of inhaled anesthetics.
 
Antiemetic / anti-nausea medication (i.e. Ondansetron) may be used prophylactically on all subjects for the prevention of nausea and vomiting at the investigator's discretion.

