4.2. Purpose

Medtronic Controlled Information

To investigate the relationship between BIS™ and inhaled anesthetics across a wide range of anesthetic concentration and hypnotic states, and to provide evidence to support BIS™ performance in use with sevoflurane, isoflurane and desflurane in combination with opioids.

5. Objectives

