5.1. Objectives

Primary Objective(s)

To determine BIS₅₀ (BIS™ value at which 50% of patients will be unresponsive at a given drug concentration)

Secondary Objective(s)

To determine BIS₉₅ (BIS™ value at which 95% of patients will be unresponsive at a given drug concentration)

To determine Prediction Probability (P_K) for correctly predicting if the subject was responsive or unresponsive.

6. Study Design

This is a prospective, randomized study to collect data to evaluate the relationship between BIS™ and inhaled anesthetics without and with opioids. Five groups of anesthetic regimens will be studied as follow:

1. Sevoflurane alone
2. Sevoflurane with Remifentanil
3. Sevoflurane with Fentanyl
4. Desflurane alone
5. Isoflurane alone

Healthy Volunteers Subjects will be randomized to an anesthetic group. The BIS™ bilateral sensor will be placed on the subject's forehead to study the effects of these drugs on the brain. Each subject will be given a sequential dose range of the target drug to achieve targeted drug concentration. At each steady-state step, and after at least 12 minutes to achieve equilibrium, the Modified Observer's Assessment of Alertness/Sedation (MOAA/S) scale will be used to perform sedation/loss of consciousness assessment, with the Picture Recall test being used in the sevoflurane, sevoflurane with remifentanil and sevoflurane with fentanyl regimens to assess the subject's level of anesthesia awareness, and Tetanic Electrical Stimulation (TES) being used if the patient is unresponsive to tactile stimuli (e.g., MOAA/S = 0, BIS™ value

< 40 at the highest concentration of anesthesia anticipated). The loss of tactile response will be defined according to the MOAA/S score value < 2 (0-1) and the presence of verbal response at values >2 (2-5).

A training group, comprising of the first 2 - 4 subjects at each site will be enrolled to train the site team on the technology and to determine the quality of data collection, as required, before randomization. Afterward, randomization will proceed based on the Sponsor's assessment of data quality.

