7.4. Intended Population

BIS™ Complete Monitoring System Indications for Use

The BIS™ EEG complete monitoring system is intended for use under the direct supervision of a licensed healthcare practitioner or by personnel trained in its proper use. The system and its associated parameters are intended for use on adult patients within a hospital or medical facility, providing patient care to monitor the state of the brain by data acquisition of EEG signals. The BIS™ index, one of the Complete Monitor output parameters, may be used as an aid in monitoring the effects of Alfentanil, Desflurane, Fentanyl, Isoflurane, Midazolam, Nitrous Oxide, Propofol, Remifentanil, Sevoflurane and its usage with these anesthetic agents may be associated with a reduction in primary anesthetic use and a reduction in emergency and recovery time. Use of the BIS™ index for monitoring to help guide anesthetic administration may be associated with the reduction of incidence of awareness with recall in adults during general anesthesia and sedation.

Currently under investigation in this study is the validation of the BIS™ index as an aid in monitoring the effects of desflurane, isoflurane, propofol and sevoflurane with balanced anesthetic techniques for adult patients.

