The Evaluation of BIS™ and Levels of Sedation in Health Volunteers (OLIVER) Study is a multi-center, prospective randomized study to collect data to evaluate the relationship between BIS™ and inhaled anesthetics without and with opioids. Healthy Volunteers will be sequentially assigned to one of the study groups of anesthetics regimens at each clinical site. The BIS™ bilateral sensor will be placed on the subject's forehead to study the effects of these drugs on the brain. Each volunteer will be given a dose range of sequences of the target drug to achieve targeted drug concentration. Five groups of anesthetics regimens will be studied as follows:

1. Sevoflurane alone
2. Sevoflurane with Remifentanil
3. Sevoflurane with Fentanyl
4. Desflurane alone
5. Isoflurane alone

At each steady-state step, and after at least 12 minutes to achieve equilibrium, the Modified Observer's Assessment of Alertness/Sedation (MOAA/S) scale will be used to perform sedation/loss of consciousness assessment. The loss of verbal response will be defined according to the MOAA/S score value < 2 (0-1) and the presence of verbal response at values ≥ 2 (2-5).

The expected duration of each subject's participation is approximately 6 hours for both enrollment and procedure. The Enrollment Visit should take approximately 2 hours to complete, and the Study Visit will be approximately 4 hours per subject. Each subject will be contacted by phone within 48 hours of the study participation. Subjects will be continuously monitored throughout the study.

This document provides a detailed description of the statistical methods and procedures to be implemented during the analysis of the study.

This statistical analysis plan (SAP) is based on Version 5.0 of the Protocol dated on 06-JAN-2022.

4 Study Objectives

4.1 Primary Objective:

To determine BIS₅₀ (BIS™ value at which 50% of subjects will be unresponsive at a given drug concentration).

4.2 Secondary Objective:

To determine BIS₉₅ (BIS™ value at which 95% of subjects will be unresponsive at a given drug concentration).

[BIS] Statistical Analysis Plan

Revision [\[x\]](#)

Page 6 of 20

Form

Medtronic

To determine Prediction Probability score (P_k) for correctly predicting if the subject was responsive or unresponsive.

5 Investigation Plan

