This is a multi-center, prospective randomized, two-stage design study to collect data to evaluate the relationship between BIS™ and inhaled anesthetics with opioids. Subjects will be enrolled in the study once all eligibility requirements for the study have been met. Subjects who give informed consent for the protocol in order to undergo screening for eligibility are not considered enrolled and should not be enrolled until the screening is completed. All subjects are healthy volunteers.

After the subjects are enrolled, they will be sequentially assigned to one of the study groups of anesthetics regimens at each clinical site. The BIS™ bilateral sensor will be placed on the subject's forehead to study the effects of these drugs on the brain. Each volunteer will be given a dose range of sequences of the target drug to achieve targeted drug concentration. Five groups of anesthetics regimens will be studied as follows:

- Sevoflurane alone
- Sevoflurane with Remifentanil
- Sevoflurane with Fentanyl
- Desflurane alone
- Isoflurane alone

At each steady-state step, and after at least 12 minutes to achieve equilibrium, the Modified Observer's Assessment of Alertness/Sedation (MOAA/S) scale will be used to perform sedation/loss of consciousness assessment. An anesthesiologist authorized to administer sedation drugs will be responsible for administering any procedural drugs for the sedation and monitoring of subject safety and physical state. All other personnel involved with the safety monitoring of subjects must be trained in and familiar with the management of recovery of sedated patients. The study site should have a setting that is fully equipped for the monitoring and support of the respiratory and cardiovascular function. Subjects will be continuously monitored throughout the study.

A two-stage design is used in this study. For each regimen group, 10 subjects will be enrolled in stage 1, and upon evaluation, up to 20 additional subjects will be enrolled in stage 2. With 5 regimen groups, a maximum of 150 subjects will be enrolled. An interim review will take place at the end of stage 1 (50 subjects, 10 subjects per regimen group). Both the primary and secondary objectives will be evaluated during the interim review, and one or more groups may be dropped upon interim results for safety concern (unacceptable safety events per clinical judgment).

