7.8 Evaluation of Objectives

The objective of this study is to investigate the relationship between BIS™ and anesthetic agents across a wide range of hypnotic states and to provide evidence to support BIS™ performance in use with these anesthetic agents.

Primary Objective:

To determine BIS₅₀ (BIS™ value at which 50% of subjects will be unresponsive at given drug concentrations).

Secondary Objective:

To determine BIS₉₅ (BIS™ value at which 95% of subjects will be unresponsive at given drug concentrations).

The logistic model (simplified Emax model) will be used to estimate the BIS™ values, along with corresponding 95% confidence intervals and standard errors.

Prediction Probability score (P_k) will be calculated following the details in the Smith's paper (Smith 1996). All technical details were provided in the Appendix in the paper. SAS procedure PROC LOGISTIC will be used to perform the calculation.

Differences in subject characteristics will be analyzed using t-test (continuous variables including age, weight and height) or Chi-square test (categorical variables including gender). The correlation coefficient for the relationship between sedation score and BIS™ value will be calculated for each group using a linear regression model. Additionally, BIS™ values and haemodynamic variables will be analyzed within the groups using analysis of variance (ANOVA) for repeated measures.

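### The stated purpose covers desflurane and isoflurane with opioids, which no regimen studies; both arms also follow propofol, which the SAP does not address

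*Protocol*

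**What the plan says.** **Purpose.** The synopsis says the study is "to provide evidence to support BIS™ performance in use with isoflurane, sevoflurane and desflurane in combination with opioids". Protocol section 4.2 again refers to "performance in use with sevoflurane, isoflurane and desflurane in combination with opioids". SAP section 5 says the data will "evaluate the relationship between BIS™ and inhaled anesthetics with opioids".

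**Design.** SAP section 3 has the data "evaluate the relationship between BIS™ and inhaled anesthetics without and with opioids", and the Protocol synopsis and section 6 word the design the same way. SAP 7.8 restates the purpose without opioids: "to provide evidence to support BIS™ performance in use with these anesthetic agents". Of the five regimens, remifentanil and fentanyl are each paired with sevoflurane. The other three are single-agent arms, among them "Desflurane alone" and its isoflurane counterpart.

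**Propofol as a study agent.** Protocol 7.4 describes the investigation as "validation of the BIS™ index as an aid in monitoring the effects of desflurane, isoflurane, propofol and sevoflurane with balanced anesthetic techniques". The synopsis indication names only the three volatiles, and no regimen has propofol as its target drug.

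**Propofol as induction.** Both the desflurane and isoflurane arms start with a propofol bolus, with supplements at the investigator's discretion. The synopsis places it 0–15 minutes before the volatile in both arms. Section 10.5 keeps 0–15 minutes for desflurane but gives 15–20 minutes for isoflurane. For both arms it adds a discretionary wait of about 15–20 minutes after laryngeal mask (LMA) placement is confirmed, aiming at MOAA/S 2 or 3.

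**Analysis.** SAP 7.2.1 fits a logistic model for unresponsiveness (MOAA/S 0–1) with one explanatory variable, BIS or log agent concentration. It derives BIS50 and EC50 for each regimen group. SAP 7.4 uses all evaluable data, without defining evaluable. The SAP does not mention propofol. Protocol section 14 leaves data exclusions to a Data Management Plan that is not among the documents.

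**The concern.** There are two separate faults.

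The first is the claim. Read plainly, the purpose attaches opioids to all three volatiles. A reader of the report or of a labelling submission could take the study as evidence for BIS with desflurane plus opioid and isoflurane plus opioid, yet no subject will be in either condition.

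The second is attribution. On early ascending steps in the desflurane and isoflurane arms, a subject may be unresponsive partly because of residual propofol. The model has nowhere to put that effect, so it is credited to a low volatile concentration, and the estimated EC50 falls. A comparison of these arms with sevoflurane alone would then set regimens that include an induction drug against one that does not.

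**Working it through.** **1. The plan's own figures.** The maximum enrolment is 5 × (10 + 20) = 150, as stated. The required 24 per regimen in SAP section 6 also reproduces: the standardised effect is 0.15 / 0.25 = 0.6, and a one-sample t-test at two-sided 0.05 first reaches 80% power at n = 24 (power 0.804). At the planned 30, power is 0.888. Nothing below changes these numbers.

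**2. Opioid exposure at 30 per regimen.**
- Sevoflurane: 3 arms × 30 = 90 subjects, of whom 2 × 30 = 60 receive an opioid.
- Desflurane and isoflurane: 2 arms × 30 = 60 subjects, of whom 0 receive an opioid.
- Propofol induction: the same 60 subjects, and no one in the sevoflurane arms.

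**3. Time from propofol to the early volatile readings.** Let s be the interval from propofol to the start of the volatile. With about 12 minutes of equilibration per step, and ignoring assessment time, reading k falls at s + 12k minutes.

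| Source | s (min) | Reading 1 | Reading 2 |
|---|---|---|---|
| Synopsis, both arms; section 10.5 desflurane if the wait is not used | 0–15 | 12–27 | 24–39 |
| Section 10.5, isoflurane interval | 15–20 | 27–32 | 39–44 |

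If the discretionary wait is used, its clock starts at LMA confirmation, so the first reading comes about 27–32 minutes after that point and somewhat later after the bolus that preceded it. Measured from the last dose, a later supplemental bolus shortens any of these intervals.

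**4. State when the volatile starts.** MOAA/S 2 or 3 counts as responsive under SAP 7.2.1, but it is a sedated state. With the wait, a subject who reaches the target is responsive when the volatile begins and then loses response under both drugs. Without the wait, no such target applies.

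**5. Which estimates are exposed.**
- EC50: unresponsiveness helped by propofol is recorded against a low volatile concentration, so the direction is downward.
- BIS50: the model relates BIS to response. Propofol shifts it only if the BIS–response relation differs between propofol and the volatile. The documents give nothing from which to judge whether it does, or in which direction.

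**6. What cannot be computed.** The documents give no propofol concentration over time and no carry-over window. The number of affected readings and the size of any EC50 or BIS50 shift therefore cannot be derived.

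**The case against.** The purpose wording changes no analysis. The objectives make no opioid claim, the design sentence is correct, and SAP section 5 lists all five regimens directly after its loose sentence. This stands: the first fault lies in the claim, and no planned test fails because of it. It still needs correcting, because the purpose is stated twice and the design cannot deliver it.

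The SAP already estimates by regimen group, and SAP 7.5 gives between-group results as estimates with intervals and p-values for reference only. The propofol induction is openly described, and no contrast of volatile against volatile is planned. This also stands, so the labelling request makes explicit what the SAP largely implies.

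The wait to MOAA/S 2 or 3 is a real mitigation, since subjects who reach it start the volatile as responders. It is only partial: it is discretionary, it appears only in section 10.5, and its target is still sedation.

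A handling rule may exist in the Data Management Plan, and the case report form may capture propofol boluses. Neither document is supplied, so the absence of a rule is not proven. What can be said is that the SAP neither states nor cites one.

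A reader might infer that the primary BIS50 in these two arms is biased, or might want to quote a percentage of contaminated readings. The documents support neither. The first needs a difference between propofol and the volatiles that they do not show, and the second needs a carry-over window that they do not give.

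**Conclusion.** The purpose is wider than the design. As written it claims opioid combinations for desflurane and isoflurane on 0 of 60 subjects, at the planned maximum of 30 per regimen. Section 7.4 similarly names propofol as under validation when no regimen targets it. These points rest on the text alone and are firm.

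The propofol point holds with moderate confidence. Both arms are propofol-induced, and the first volatile reading falls roughly 12–32 minutes after propofol across the stated intervals, assuming 12 minutes per step and no later supplement. The SAP has no stated way of separating the two drugs. The planned EC50, which is a SAP estimate but not a study objective, may be pulled down by an amount that cannot be computed. No bias in the primary BIS50 is shown.

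The sponsor should correct the wording and add a prespecified check. The sample size and the primary estimate can stay as they are.

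**What to change.** 1. **Purpose.** Restate the synopsis purpose, Protocol 4.2 and SAP section 5 as: sevoflurane without and with remifentanil or fentanyl, and desflurane and isoflurane after propofol induction, without opioids. Reconcile Protocol 7.4 with the synopsis indication on propofol.
2. **Labels.** Call the two arms propofol-induced in the SAP and reports, and describe between-group results as comparisons of regimens.
3. **Sensitivity analysis.** Keep the all-step fit as primary. In SAP 7.2.1 prespecify, for these two arms only, EC50 and BIS50 fits that leave out ascending steps within a stated time of the last propofol bolus. If the Data Management Plan already has such a rule, cite it. A descending-steps-only comparison across all five arms is not advised: descent stops when consciousness returns, so the stopping depends on the response and could itself distort the logistic fit.
4. **Data capture.** Confirm that the case report form records the time and dose of every propofol bolus, supplements included. Section 10.5 lists drug infusions and changes in subject management, and the synopsis mentions lidocaine "to aid in the infusion of propofol for subject's comfort", so capture may be intended, but it is not stated for boluses.
5. **Timing, as a clinical-management item.** Reconcile the propofol-to-isoflurane interval (0–15 minutes in the synopsis, 15–20 in section 10.5). In the section 10.5 desflurane text, also reconcile the 0–15 minute interval with the 15–20 minute wait. This review does not say which is right.

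The cost is wording, a case report form clarification and extra model runs. The claim becomes narrower. The sensitivity fits lose precision: each excluded step is one of 6 listed ascending steps for desflurane or 5 for isoflurane, and the steps lost are the lowest concentrations.
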